### 6.5 Administration of Pembrolizumab Beyond Progression

If the initial week 12 scan shows disease progression per RECIST 1.1, patients are allowed to continue treatment until progression is confirmed again at a subsequent 4-6 week later, to account for atypical response patterns. If the repeat imaging shows evidence of disease stabilization or objective response (relative to the previous scan that showed PD) as per RECIST 1.1, pembrolizumab may be continued per treatment calendar. However, if the repeat assessment shows disease progression relative to the previous scan that showed PD, then pembrolizumab should be discontinued; The minimum criteria to continue must include absence of symptoms/signs of disease progression, no decline in performance status, and absence of rapid progression of disease at critical anatomic sites (i.e cord compression) requiring urgent alternative medical intervention.

## 7.0 DOSE MODIFICATION

### 7.0.1 Dose Modification, General

Adverse events (both non-serious and serious) associated with pembrolizumab exposure may represent an immunologic etiology. These adverse events may occur shortly after the first dose, or several months after the last dose of treatment. Pembrolizumab must be withheld for drug-related toxicities and severe or life-threatening AEs as per **Table 6** and **Table 7** below. See Section 8.0 and 9.0 as well as Events of Clinical Interest Guidance Document for supportive care guidelines, including use of corticosteroids (less than or equal to 10 mg prednisone equivalent at time of start of treatment is ok).

### 7.0.1 Dose Modification, Non CNS toxicities

**Table 6 Dose Modification Guidelines for Drug-Related Adverse Events**

Toxicity	Hold Treatment For Grade	Timing for Restarting Treatment	Treatment Discontinuation
Diarrhea/Colitis	2-3	Toxicity resolves to Grade 0-1	Toxicity does not resolve within 12 weeks of last dose or inability to reduce corticosteroid to 10 mg or less of prednisone or equivalent per day within 12 weeks
	4	Permanently discontinue	Permanently discontinue
AST, ALT, or Increased Bilirubin	2	Toxicity resolves to Grade 0-1	Toxicity does not resolve within 12 weeks of last dose
	3-4	Permanently discontinue (see exception below) a	Permanently discontinue
Type 1 diabetes mellitus (if new onset) or Hyperglycemia	T1DM or 3-4	Hold pembrolizumab for new onset Type 1 diabetes mellitus or Grade 3-4 hyperglycemia associated with evidence of beta cell failure	Resume pembrolizumab when patients are clinically and metabolically stable

Toxicity	Hold Treatment For Grade	Timing for Restarting Treatment	Treatment Discontinuation
Hypophysitis	2-4	Toxicity resolves to Grade 0-1. Therapy with pembrolizumab can be continued while endocrine replacement therapy is instituted	Toxicity does not resolve within 12 weeks of last dose or inability to reduce corticosteroid to 10 mg or less of prednisone or equivalent per day within 12 weeks
Hyperthyroidism	3	Toxicity resolves to Grade 0-1	Toxicity does not resolve within 12 weeks of last dose or inability to reduce corticosteroid to 10 mg or less of prednisone or equivalent per day within 12 weeks
	4	Permanently discontinue	Permanently discontinue
Hypothyroidism		Therapy with pembrolizumab can be continued while thyroid replacement therapy is instituted	Therapy with pembrolizumab can be continued while thyroid replacement therapy is instituted
Infusion Reaction	2 b	Toxicity resolves to Grade 0-1	Permanently discontinue if toxicity develops despite adequate premedication
	3-4	Permanently discontinue	Permanently discontinue
Pneumonitis	2	Toxicity resolves to Grade 0-1	Toxicity does not resolve within 12 weeks of last dose or inability to reduce corticosteroid to 10 mg or less of prednisone or equivalent per day within 12 weeks
	3-4	Permanently discontinue	Permanently discontinue
Renal Failure or Nephritis	2	Toxicity resolves to Grade 0-1	Toxicity does not resolve within 12 weeks of last dose or inability to reduce corticosteroid to 10 mg or less of prednisone or equivalent per day within 12 weeks
	3-4	Permanently discontinue	Permanently discontinue
All Other Drug-Related Toxicity c	3 or Severe	Toxicity resolves to Grade 0-1	Toxicity does not resolve within 12 weeks of last dose or inability to reduce corticosteroid to 10 mg or less of prednisone or equivalent per day within 12 weeks
	4	Permanently discontinue	Permanently discontinue
Note: Permanently discontinue for any severe or Grade 3 drug-related AE that recurs or any life-threatening event. a For patients with liver metastasis who begin treatment with Grade 2 AST or ALT, if AST or ALT increases by greater than or equal to 50% relative to baseline and lasts for at least 1 week then patients should be discontinued. b If symptoms resolve within one hour of stopping drug infusion, the infusion may be restarted at 50% of the original infusion rate (e.g., from 100 mL/hr to 50 mL/hr). Otherwise dosing will be held until symptoms resolve and the subject should be premedicated for the next scheduled dose; Refer to Table – Infusion Treatment Guidelines for further management details. c Patients with intolerable or persistent Grade 2 drug-related AE may hold study medication at physician discretion. Permanently discontinue study drug for persistent Grade 2 adverse reactions for which treatment with study drug has been held, that do not recover to Grade 0-1 within 12 weeks of the last dose.			

Dosing interruptions are permitted in the case of medical / surgical events or logistical reasons not related to study therapy (e.g., elective surgery, unrelated medical events, patient vacation, and/or holidays). Subjects should be placed back on study therapy within 3 weeks +/- 7 days of the scheduled interruption, unless otherwise discussed with the Sponsor. The reason for interruption should be documented in the patient's study record.

### 7.0.2 Dose Modification, CNS toxicities

Toxicity	Hold Treatment For Grade	Timing for Restarting Treatment	Discontinue Subject
Central Nervous	2-3	Toxicity resolves to Grade 0-1.	Toxicity does not resolve within 12 weeks of last dose or inability to reduce corticosteroid to

Toxicity	Hold Treatment For Grade	Timing for Restarting Treatment	Discontinue Subject
System Necrosis		(see exception below) 	1 mg or less of dexamethasone or equivalent per day within 12 weeks.
	4	Permanently discontinue	Permanently discontinue
Seizure	2-3	Toxicity resolves to Grade 0-1	Toxicity does not resolve within 12 weeks of last dose.
	4	Permanently discontinue	Permanently discontinue
Cognitive Impairment or Cognitive Disturbance	2-3	Toxicity resolves to Grade 0-1	Toxicity does not resolve within 12 weeks of last dose or inability to reduce corticosteroid to 1 mg or less of dexamethasone or equivalent per day within 12 weeks.
	4	Permanently discontinue	Permanently discontinue
Stroke	2	Toxicity resolves to Grade 0-1	Toxicity does not resolve within 12 weeks of last dose
	3-4	Permanently discontinue	Permanently discontinue

 Patients with intolerable or persistent Grade 2 drug-related AE may hold study medication at physician discretion. Permanently discontinue study drug for persistent Grade 2 adverse reactions for which treatment with study drug has been held, that do not recover to Grade 0-1 within 12 weeks of the last dose.

## 8.0 DOSE LIMITING TOXICITIES

### Dose limiting toxicity definition

Dose limiting toxicity is defined as symptomatic (i.e, presenting with neurological symptoms) radiation necrosis rate that exceeds 30% at 6 months as outlined in section 2; Imaging evidence post SRS (MRI and/or PET) must confirm the presence of radionecrosis along with associated clinical symptoms. The symptoms can be described as “Nervous system disorders” with a CTCAE 4.0 grade 3 or 4 or higher.

Please see APPENDIX 1 for list of all CNS Nervous system disorders and appropriate grading. Below is a table of the most common CNS Nervous System Disorders;

Adverse Event	Grade 1	Grade 2	Grade 3	Grade 4	Grade 5
Central Nervous System Necrosis	Asymptomatic; clinical or diagnostic observations only; intervention not indicated	Moderate symptoms; corticosteroids indicated	Severe symptoms; medical intervention indicated	Life-threatening consequences; urgent intervention indicated	Death

Seizure (Definition: A disorder characterized by a sudden, involuntary skeletal muscular contractions of cerebral or brain stem origin.)	Brief partial seizure; no loss of consciousness	Brief generalized seizure	Multiple seizures despite medical intervention	Life-threatening; prolonged repetitive seizures repetitive seizures	Death
Cognitive Impairment	Mild inattention or decreased level of concentration	Moderate impairment in attention or decreased level of concentration; limiting instrumental ADL	Severe impairment in attention or decreased level of concentration; limiting self care ADL		
Cognitive Disturbance	Mild cognitive disability; not interfering with work/school/life performance; specialized educational services/devices not indicated	Moderate cognitive disability; interfering with work/school/life performance but capable of independent living; specialized resources on part time basis indicated	Severe cognitive disability; significant impairment of work/school/life performance		
Stroke	Asymptomatic or mild neurologic deficit; radiographic findings only	Moderate neurologic deficit	Severe neurologic deficit	Life-threatening consequences; urgent intervention indicated	Death
Intracranial Hemorrhage (A disorder characterized by bleeding from the cranium.)	Asymptomatic; clinical or diagnostic observations only; intervention not indicated	Moderate symptoms; medical intervention indicated	Ventriculostomy, ICP, monitoring, intraventricular thrombolysis, or operative intervention indicated	Life-threatening consequences; urgent intervention indicated	Death
Headache (definition: A disorder characterized by a sensation of marked discomfort in various parts of the head, not confined to the area of distribution of any nerve.)	Mild Pain	Moderate pain, limiting instrumental ADL	Severe pain, limiting self care ADL		

**Product:** Pembrolizumab (MK-3475, IND 130757)  
**Protocol/Amendment No.:** Rad3179-16 (MK-3475-423),  
v.12/03/2019

## 9.0 SUPPORTIVE CARE

### 9.1.1 Supportive Care, General

Subjects should receive appropriate supportive care measures as deemed necessary by the treating investigator. Suggested supportive care measures for the management of adverse events with potential immunologic etiology are outlined below. Where appropriate, these guidelines include the use of oral or intravenous treatment with corticosteroids as well as additional anti-inflammatory agents if symptoms do not improve with administration of corticosteroids. Note that several courses of steroid tapering may be necessary as symptoms may worsen when the steroid dose is decreased. For each disorder, attempts should be made to rule out other causes such as metastatic disease or bacterial or viral infection, which might require additional supportive care. The treatment guidelines are intended to be applied when the investigator determines the events to be related to pembrolizumab.

Note: if after the evaluation the event is determined not to be related, the investigator is instructed to follow the ECI reporting guidance but does not need to follow the treatment guidance (as outlined in the ECI guidance document). Refer to Section 7.0 for dose modification.

It may be necessary to perform conditional procedures such as bronchoscopy, endoscopy, or skin photography as part of evaluation of the event. Suggested conditional procedures, as appropriate, can be found in the ECI guidance document.

### 9.1.2 Supportive Care, Guidelines for Non-CNS toxicities

- **Pneumonitis:**

- For **Grade 2 events**, treat with systemic corticosteroids. When symptoms improve to Grade 1 or less, steroid taper should be started and continued over no less than 4 weeks.
- For **Grade 3-4 events**, immediately treat with intravenous steroids. Administer additional anti-inflammatory measures, as needed.
- Add prophylactic antibiotics for opportunistic infections in the case of prolonged steroid administration.

- **Diarrhea/Colitis:**

Subjects should be carefully monitored for signs and symptoms of enterocolitis (such as diarrhea, abdominal pain, blood or mucus in stool, with or without fever) and of bowel perforation (such as peritoneal signs and ileus).

- All subjects who experience diarrhea/colitis should be advised to drink liberal quantities of clear fluids. If sufficient oral fluid intake is not feasible, fluid and electrolytes should be substituted via IV infusion. For Grade 2 or higher diarrhea, consider GI consultation and endoscopy to confirm or rule out colitis.
- For **Grade 2 diarrhea/colitis** that persists greater than 3 days, administer oral corticosteroids.

- For **Grade 3 or 4 diarrhea/colitis** that persists > 1 week, treat with intravenous steroids followed by high dose oral steroids.
- When symptoms improve to Grade 1 or less, steroid taper should be started and continued over no less than 4 weeks.
- **Type 1 diabetes mellitus (if new onset, including diabetic ketoacidosis [DKA]) or ≥ Grade 3 Hyperglycemia, if associated with ketosis (ketonuria) or metabolic acidosis (DKA)**
  - For **T1DM or Grade 3-4 Hyperglycemia**
    - Insulin replacement therapy is recommended for Type I diabetes mellitus and for Grade 3-4 hyperglycemia associated with metabolic acidosis or ketonuria.
    - Evaluate patients with serum glucose and a metabolic panel, urine ketones, glycosylated hemoglobin, and C-peptide.
- **Hypophysitis:**
  - For **Grade 2** events, treat with corticosteroids. When symptoms improve to Grade 1 or less, steroid taper should be started and continued over no less than 4 weeks. Replacement of appropriate hormones may be required as the steroid dose is tapered.
  - For **Grade 3-4** events, treat with an initial dose of IV corticosteroids followed by oral corticosteroids. When symptoms improve to Grade 1 or less, steroid taper should be started and continued over no less than 4 weeks. Replacement of appropriate hormones may be required as the steroid dose is tapered.
- **Hyperthyroidism or Hypothyroidism:**

Thyroid disorders can occur at any time during treatment. Monitor patients for changes in thyroid function (at the start of treatment, periodically during treatment, and as indicated based on clinical evaluation) and for clinical signs and symptoms of thyroid disorders.

  - **Grade 2** hyperthyroidism events (and **Grade 2-4** hypothyroidism):
    - In hyperthyroidism, non-selective beta-blockers (e.g. propranolol) are suggested as initial therapy.
    - In hypothyroidism, thyroid hormone replacement therapy, with levothyroxine or liothyronine, is indicated per standard of care.
  - **Grade 3-4** hyperthyroidism
    - Treat with an initial dose of IV corticosteroid followed by oral corticosteroids. When symptoms improve to Grade 1 or less, steroid taper should be started and continued over no less than 4 weeks. Replacement of appropriate hormones may be required as the steroid dose is tapered.

- **Hepatic:**
  - For **Grade 2** events, monitor liver function tests more frequently until returned to baseline values (consider weekly).
    - Treat with IV or oral corticosteroids
  - For **Grade 3-4** events, treat with intravenous corticosteroids for 24 to 48 hours.
  - When symptoms improve to Grade 1 or less, a steroid taper should be started and continued over no less than 4 weeks.
  
- **Renal Failure or Nephritis:**
  - For **Grade 2** events, treat with corticosteroids.
  - For **Grade 3-4** events, treat with systemic corticosteroids.
  - When symptoms improve to Grade 1 or less, steroid taper should be started and continued over no less than 4 weeks.

**Management of Infusion Reactions:** Signs and symptoms usually develop during or shortly after drug infusion and generally resolve completely within 24 hours of completion of infusion. **Table 7** below shows treatment guidelines for subjects who experience an infusion reaction associated with administration of pembrolizumab (MK-3475).

**Table 7** Infusion Reaction Treatment Guidelines

NCI CTCAE Grade	Treatment	Premedication at subsequent dosing
Grade 1 Mild reaction; infusion interruption not indicated; intervention not indicated	Increase monitoring of vital signs as medically indicated until the subject is deemed medically stable in the opinion of the investigator.	None
Grade 2 Requires infusion interruption but responds promptly to symptomatic treatment (e.g., antihistamines, NSAIDS, narcotics, IV fluids); prophylactic medications indicated for <=24 hrs	Stop Infusion and monitor symptoms. Additional appropriate medical therapy may include but is not limited to: IV fluids Antihistamines NSAIDS Acetaminophen Narcotics Increase monitoring of vital signs as medically indicated until the subject is deemed medically stable in the opinion of the investigator. If symptoms resolve within one hour of stopping drug infusion,	Subject may be premedicated 1.5h (± 30 minutes) prior to infusion of pembrolizumab (MK-3475) with:  Diphenhydramine 50 mg po (or equivalent dose of antihistamine).  Acetaminophen 500-1000 mg po (or equivalent dose of antipyretic).

NCI CTCAE Grade	Treatment	Premedication at subsequent dosing
	
the infusion may be restarted at 50% of the original infusion rate (e.g., from 100 mL/hr to 50 mL/hr). Otherwise dosing will be held until symptoms resolve and the subject should be premedicated for the next scheduled dose.
 
Subjects who develop Grade 2 toxicity despite adequate premedication should be permanently discontinued from further trial treatment administration.
	

Grades 3 or 4  Grade 3:  Prolonged (i.e., not rapidly responsive to symptomatic medication and/or brief interruption of infusion); recurrence of symptoms following initial improvement; hospitalization indicated for other clinical sequelae (e.g., renal impairment, pulmonary infiltrates)  Grade 4:  Life-threatening; pressor or ventilatory support indicated
	
Stop Infusion.  Additional appropriate medical therapy may include but is not limited to:  IV fluids  Antihistamines  NSAIDS  Acetaminophen  Narcotics  Oxygen  Pressors  Corticosteroids  Epinephrine
 
Increase monitoring of vital signs as medically indicated until the subject is deemed medically stable in the opinion of the investigator.  Hospitalization may be indicated.  Subject is permanently discontinued from further trial treatment administration.
	
No subsequent dosing


Appropriate resuscitation equipment should be available in the room and a physician readily available during the period of drug administration.
		

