### 9.1.3 Supportive Care, Guidelines for CNS toxicities

- **Central Nervous System Necrosis:**
  - For **Grade 2 events**, treat with systemic steroids, pentoxifylline and vitamin E. Consider starting with doses less than dexamethasone 6mg PO daily (2 mg TID), if clinically acceptable and indicated.
  - For **Grade 3-4 events**, immediately treat with intravenous steroids. Administer additional anti-inflammatory measures, such as hyperbaric oxygen and/or surgical intervention.
  - When symptoms improve to Grade 1 or less, steroid taper should be started immediately, continued over no less than 4 weeks.
  - It may be that a patient may need low doses of steroids long term, in that case, the goal is to achieve the lowest tolerated steroid levels to manage the radiation necrosis.
- **Seizure:**
  - For **Grade 1-2 events**, treat with oral anti-seizure medications. If clinically safe and acceptable, consider starting with levetiracetam 1000mg BID, or alternative.
  - For **Grade 3-4 events**, treat with oral and/or IV anti corticosteroids with consideration for surgery, if clinically feasible.
  - When symptoms improve to Grade 1 or less, steroid taper should be started and continued over no less than 4 weeks.
- **Cognitive Impairment or Cognitive Disturbance**
  - For **Grade 2 events**, treat with systemic steroids. Consider starting with doses less than 6 mg PO dexamethasone (2 mg TID), if clinically acceptable and indicated. Memantine or other Alzheimer related medication can also be considered.
  - For **Grade 3-4 events**, immediately treat with intravenous steroids.
  - When symptoms improve to Grade 1 or less, steroid taper should be started and continued over no less than 4 weeks.

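### Section 9.1.2 sets a later steroid trigger for grade 3-4 diarrhea/colitis (more than 1 week) than for grade 2 (more than 3 days), and no other grade 3-4 steroid rule in section 9 has a wait

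*Combined protocol and SAP*

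**What the plan says.** Section 9.1.2 treats diarrhea/colitis in two adjacent bullets. A grade 2 event "that persists greater than 3 days, administer oral corticosteroids". A grade 3 or 4 event "that persists > 1 week, treat with intravenous steroids followed by high dose oral steroids". The same block asks staff to watch for signs of enterocolitis "and of bowel perforation (such as peritoneal signs and ileus").

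The other grade 3-4 steroid rules read differently. In section 9.1.2, pneumonitis says "immediately treat with intravenous steroids. Administer additional anti-inflammatory measures, as needed", hypophysitis says "treat with an initial dose of IV corticosteroids followed by oral corticosteroids", and hepatic events say "treat with intravenous corticosteroids for 24 to 48 hours". In section 9.1.3, CNS necrosis says "immediately treat with intravenous steroids. Administer additional anti-inflammatory measures, such as hyperbaric oxygen and/or surgical intervention".

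Section 9.1.1 sets the status of all this text: "Suggested supportive care measures for the management of adverse events with potential immunologic etiology are outlined below". It leaves care to the treating investigator, asks that other causes such as infection be ruled out, and applies the guidelines once an event is judged related to pembrolizumab.

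**The concern.** Within one toxicity, the time to the suggested steroid start lengthens as the grade rises. Read literally, a patient whose colitis is grade 3-4 from onset waits longer for steroids than a patient with a moderate event, in a condition where the protocol itself names bowel perforation as something to look for. The wait also sits badly with the grading table in section 13.2.4, where grade 3 indicates hospitalization and grade 4 indicates urgent intervention. The bullet covers both grades. What is at stake is the safety of a small number of patients; no estimate or decision rule in section 14 depends on it.

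**Working it through.** **1. The two triggers.** More than 3 days, in whole days, means from day 4 (grade 2, oral steroids). More than 1 week means from day 8 (grade 3-4, IV then high-dose oral). Difference: 8 − 4 = 4 days, in the wrong direction.

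**2. All grade 3-4 steroid rules in section 9.**

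| Section | Toxicity | Wait before steroids |
|---|---|---|
| 9.1.2 | Pneumonitis | None (immediate) |
| 9.1.2 | Diarrhea/colitis | **More than 1 week** |
| 9.1.2 | Hypophysitis | None stated |
| 9.1.2 | Hyperthyroidism | None stated |
| 9.1.2 | Hepatic | None stated (24 to 48 hours is a treatment duration) |
| 9.1.2 | Renal failure/nephritis | None stated |
| 9.1.3 | CNS necrosis | None (immediate) |
| 9.1.3 | Seizure | None stated (the drug wording is garbled) |
| 9.1.3 | Cognitive impairment/disturbance | None (immediate) |

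That is 6 + 3 = 9 rules, of which 1 has a wait. Without the garbled seizure rule it is 1 of 8. Counting the optional corticosteroid entry for infusion reactions in section 9.1.2, Table 7, it is 1 of 10. Diabetes/hyperglycemia and hypothyroidism are left out because their rules do not use steroids. Diarrhea/colitis stands alone under every count.

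**3. Does other text override the wait?** Section 7, Table 6 holds pembrolizumab at grade 2-3 diarrhea/colitis and stops it at grade 4, but gives no steroid start time. Section 6.4.2 permits systemic steroids for suspected immune events but does not prompt their use. Nothing in the file supplies an earlier trigger.

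**4. How many patients?** Inputs: 30 patients (section 1.0); grade 3 diarrhea reported as 1% in a melanoma trial (section 4.3.2) of 135 patients (section 4.2.1). Section 4.3.2 also shows 2 renal failure cases as 1%, so a rounded 1% of 135 fits 1 or 2 cases. Expected number = 30p; chance of at least one = 1 − (1 − p)^30.

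| Assumed p | Expected in 30 | Chance of at least one |
|---|---|---|
| 1/135 = 0.74% | 0.22 | 1 − (134/135)^30 = 20% |
| 1% | 0.30 | 1 − 0.99^30 = 26% |
| 2/135 = 1.48% | 0.44 | 1 − (133/135)^30 = 36% |

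These are not upper bounds. The 95% Clopper-Pearson interval for 2/135 is 0.18% to 5.25%, and 30 × 0.0525 ≈ 1.6 patients. For that trial, section 4.3.2 gives no grade 4 diarrhea rate and does not list colitis.

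**The case against.** The case for leaving the text alone, or giving it low priority, has several parts.

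- **The guidance is advisory.** The bullet does not forbid earlier steroids, section 9.1.1 defers to the investigator, and section 6.4.2 allows steroids for immune events with no time condition. This limits harm, but a suggestion exists to steer staff, and this one steers toward later treatment of the sicker patient.
- **Other safeguards act sooner.** GI consultation and endoscopy are to be considered from grade 2 with no wait, fluids and electrolytes are covered, drug is held or stopped, grade 3 indicates hospitalization, and an inpatient admission is a serious adverse event reportable to the sponsor within 24 hours (section 13.2.3.1). All true. A week of unnoticed severe colitis is unlikely, but none of these measures starts steroids.
- **The lag is not universal.** A patient who spends more than 3 days at grade 2 before worsening has already met the oral trigger. The 4-day lag applies to events that reach grade 3-4 before that point. This stands and reduces the number affected.
- **Being unusual among organs proves little.** Diarrhea/colitis is also the only grade 2 steroid rule with a wait, and nobody objects to that. This is fair: the stronger evidence is the reversal within diarrhea/colitis and the clash with the grade 4 definition. The count is supporting evidence.
- **The rate may be too high for this trial.** In section 4.3.2 the second melanoma trial lists grade 3-4 diarrhea below 1%. The 495-patient NSCLC study does not include diarrhea among its most common grade 3 or higher events, where the smallest entry is 0.8% (30 × 0.008 = 0.24 patients). Grade 3-4 events overall were dose related in the 135-patient trial, at 23% for 10 mg/kg every 2 weeks against 4-9% for the every-3-week cohorts, and this trial doses every 3 weeks. These points stand and pull the expected number down.
- **The separate Events of Clinical Interest guidance is not in the file.** It may already say something better. If so, staff hold two conflicting instructions, which is another reason to correct this one.

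**Conclusion.** The concern holds. The grade 3-4 diarrhea/colitis bullet is wrong as written: it delays the suggested steroid start by 4 days relative to grade 2, it is the only one of nine comparable rules with a wait, and it is inconsistent with the protocol's own definition of grade 4. The plan gives no reason for the exception.

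The consequence is rare but potentially severe. The figure of 0.22 to 0.44 expected grade 3 cases among 30 patients assumes that the rate in the 135-patient melanoma trial carries over to this mixed melanoma and NSCLC population on 200 mg every 3 weeks. The other data in section 4.3.2 suggest it may be lower, and only some of those cases would meet the reversed trigger. The sampling uncertainty around so few events still allows a higher number. It should be corrected because the error bears on patient safety and is easily removed.

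**What to change.** In section 9.1.2, delete the more-than-1-week persistence condition from the grade 3 or 4 diarrhea/colitis bullet, so that IV steroids followed by high-dose oral steroids are suggested once the event reaches that grade. Section 9.1.1 already confines this to events judged related to pembrolizumab and asks for other causes to be ruled out, so no further qualifier is needed. The grade 2 bullet can stay.

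Moving the grade 3-4 trigger to more than 3 days would remove the reversal, but would still delay treatment of a grade 4 event, so deletion is preferable. While editing, check that the Events of Clinical Interest guidance document agrees.

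The cost is one phrase in a protocol amendment, with no added procedures, visits or patients.
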